3.1.2 DOSE-ESCALATION PLAN

Oprozomib Tablets

Prior to Amendment 3, oprozomib doses were escalated in sequential groups of 3 subjects with expansion up to 6 subjects, if a DLT was observed using Oprozomib Tablets. The initial cohorts of the study will be entered at a dose level of 210 mg for both schedules. All subsequent cohorts will be escalated by 30 mg until the MTD is determined.

In the event that the initial cohort that received the 210 mg dose is found to exceed the MTD (the highest dose at which a DLT is observed in fewer than 2 of 6 subjects), dosing will proceed at 180 mg or lower, as agreed with the Cohort Safety Review Committee.

Oprozomib ER Tablets

The introduction of Oprozomib ER Tablets into the study and determination of MTD of this formulation for the 5/14 and 2/7 schedules are described below:

5/14 Schedule

For the 5/14 once-daily dosing schedule, Oprozomib ER Tablets will be introduced with step-up dosing as described below. Determination of the MTD for step-up dosing will proceed in the following manner:

- The first cohort will enroll 6 subjects using step-up dosing. Subjects will receive 1 cycle at the 150 mg dose and then step-up to the 180 mg dose for subsequent cycles (150/180 mg). The DLT period will begin in Cycle 2 (the first cycle of dosing at the step-up dose level).
- For the next cohort, 6 subjects will be dosed with continuous dosing of 180 mg (Table 4, Cohort 502) of Oprozomib ER Tablets and assessed for DLTs to determine safety of this dose level.
- Further escalation will be based on the following:
 - If < 2 DLTs are observed in the continuous dosing cohort of 180 mg in Cycle 1, dose escalation may continue but will revert to step-up dosing (i.e., 150/210 mg, 150/240 mg, etc.) unless an alternate RP2D has been determined by the CSRC and sponsor.
 - If > 2 DLTs are observed, further escalation will not be conducted.

2/7 Schedule

For the 2/7 once daily dosing schedule, Oprozomib ER Tablets will be introduced into subsequent cohorts where no subjects have been enrolled unless the MTD for continuous dosing for Oprozomib Tablets has been previously determined prior to the introduction of the new tablets. One of the following 2 scenarios will be utilized to introduce Oprozomib ER Tablets into the dose escalation schema:

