NA	404 ^b	360	20

CSRC = Cohort Safety Review Committee; DLT = dose-limiting toxicity; MTD = maximum tolerated dose; NA = not applicable.

Note: This table is for illustrative purposes.

^a If DLTs are observed in 2 or more subjects at the first dose level of 210 mg, dosing of Cohort -301 or -401 will proceed at 180 mg, or a lower dose as agreed with the CSRC and sponsor, and may be expanded up to 6 evaluable subjects.

^b Additionally, subsequent cohorts of 3 subjects will continue to be enrolled with doses escalated by 30 mg until the MTD (the highest dose at which a DLT is observed in fewer than 2 of 6 evaluable subjects) is defined.

Table 4: Dose-Escalation Schemes Using Oprozomib Extended Release Tablets: 5 Consecutive Day Bimonthly Schedule

5 Consecutive Day Bimonthly Schedule	Oprozomib Daily Dose Cycle 1 (mg)	Oprozomib Daily Dose to be Studied Cycles 2+ (mg)	Dexamethasone Dose (mg)
Step-up dosing with initial 1 cycle of 150 mg			
501 ^a	150	180	20
Continuous dosing			
502	180	180	20
Step-up dosing with initial 1 cycle of 150 mg			
503	150	210	20
504	150	240	20
505	150	270	20

^a Cohort will be dosed at 150 mg for 1 cycle and then increased to the step-up dose to be studied on Cycle 2 for the 5/14 once-daily dosing schedule. This is just an example and not meant to be all encompassing for further dose escalation beyond 270 mg. Dose-limiting toxicity period will be 1 cycle (Cycle 1 for continuous dosing or Cycle 2 for step-up dosing).

**Table 5: Dose-Escalation Schemes for Oprozomib Extended Release Tablets:
2 Consecutive Day Weekly Schedule**

2 Consecutive Day Weekly Schedule	Oprozomib Daily Dose Cycle 1 (mg)	Oprozomib Daily Dose to be Studied Cycles 2+ (mg)	Dexamethasone Dose (mg)
Cohort for continuous dosing			
601 Repeat at continuous dosing MTD ^b unless MTD achieved with OPZ ER Tablets	MTD	MTD ^b	20
Step-up dosing with initial 1 cycle 240 mg ^a			
602	240	MTD ^b	20
603	240	MTD ^b + 30	20
604	240	MTD ^b + 60	20
605	240	MTD ^b + 90	20

^a Cohorts will be dosed at 240 mg for 1 cycle and then increased to the step-up dose to be studied on Cycle 2 for the 2/7 once-daily dosing schedule. Dose-limiting toxicity period will be 1 cycle (Cycle 1 for continuous dosing or Cycle 2 for step-up dosing).

^b MTD for continuous dosing is to be determined.

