6.3 DOSE-LIMITING TOXICITY

Subjects will be evaluated for DLT according to the NCI-CTCAE (Version 4.03). Subjects with SD or better may continue treatment.

During the Phase 1b portion, assessment of DLTs will occur during the first 14 days of treatment with continuous dosing (Cycle 1) or during the first 14 days of treatment with the step-up dose to be studied during the 2-week assessment period (Cycle 2). Any subject who develops a DLT during the assessment period after receiving at least 1 dose of oprozomib in the

assessment period will be considered evaluable. Any subject who does not develop a DLT, but has not received all planned doses of oprozomib and dexamethasone, will be considered unevaluable and will be replaced.

Guidelines for withholding study treatment, including treatment delays, reintroduction, and discontinuation, are described in [Section 6.4.1](#). “Study drug-related” is defined as a reasonable likelihood of clinical causality based on time of event, biology, and dechallenge improvement, and that the AE was not likely explained by the subject’s clinical state, underlying disease, concomitant medication, or study/nonstudy procedure. For the purposes of this study, a DLT is defined as any of the following treatment-related events occurring in the first 14 days of treatment, with treatment at the dose to be studied (i.e., Cycle 1 for continuous dosing or Cycle 2 for step-up dosing):

Any \geq Grade 3 nonhematologic AE, with the following exceptions or qualifications:

- \geq Grade 4 abnormalities in serum creatinine or electrolytes will be considered a DLT.
- \geq Grade 3 acute kidney injury, defined as serum creatinine $> 3 \times$ baseline or > 4.0 mg/dL of any duration will be considered a DLT.
- Grade 3 nausea, vomiting, diarrhea, or constipation will be considered a DLT only if lasting for > 7 days despite optimal supportive care, including (at a minimum) a 5-HT₃ antagonist and aprepitant or fosaprepitant for nausea and vomiting, and loperamide (e.g., Imodium), and diphenoxylate/atropine (e.g., Lomotil) for diarrhea.
- Grade 3 fatigue lasting > 14 days will be considered a DLT.
- Asymptomatic Grade 3 hypophosphatemia lasting less than 24 hours will not be considered a DLT.
- \geq Grade 3 dexamethasone-related toxicities will not be considered DLTs.

Any of the following hematologic AEs will be considered a DLT:

- Grade 4 neutropenia: ANC < 500 cells/mcL lasting ≥ 7 days

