10.1 STUDY ENDPOINTS

Primary Endpoints

Phase 1b

- Dose-limiting toxicities identified to determine the MTD and RP2D, defined as the highest dose at which < 33% of subjects experience DLTs after 1 cycle (14 days Cycle 1 for continuous dosing and Cycle 2 for step-up dosing) of treatment.
- Safety and tolerability

Phase 2

- Overall response status, to determine whether a subject has a best response of sCR, CR, VGPR, or PR, as defined by IMWG-URC, and MR or nCR per EBMT criteria ([Appendix H](#))
- Safety and tolerability

Secondary Endpoints

Phase 1b/2

- Pharmacokinetics of Oprozomib Tablets and Oprozomib ER Tablets

Phase 2

- Clinical benefit response status, to determine whether a subject has a best response of sCR, CR, VGPR, or PR, as defined by IMWG-URC, and MR or nCR per EBMT criteria ([Appendix H](#))
- Duration of response, defined as the time from first evidence of PR or better to confirmation of disease progression or death due to any cause
- Progression-free survival, defined as the time from the start of treatment to disease

- progression or death due to any cause
- Time to progression, defined as the time from first dose to disease progression
 - Time to response, defined as time from the start of study treatment until the start of the first confirmed response (PR or better).

Exploratory Endpoints

Phase 1b/2

- Pharmacodynamics and proteomic biomarkers
- Genomic biomarkers that may potentially predict for response and resistance following treatment with proteasome inhibitors

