10.3.3 SAFETY ANALYSIS

Safety and tolerability assessments will include extent of exposure to study treatment, AEs (including the DLT assessment period DLTs and SAEs), laboratory values, vital sign results, and ECGs. Safety data will be examined on an ongoing basis to ensure subject safety.

Extent of exposure to the study treatment will be summarized using descriptive statistics (n, mean, standard deviation, median, and range). Percent of subjects and number of cycles with dose holds and reductions will be calculated by treatment group.

Adverse events will be coded using MedDRA. Treatment-emergent AEs are defined as AEs occurring from the first dose of study treatment through 30 days after the last dose of study treatment. An AE that is present before the first administration of study treatment and subsequently worsens in severity between the first dose of study treatment and 30 days after the last dose of study treatment is also considered to be treatment emergent. Adverse events will be summarized by MedDRA system organ class and preferred term for the number and percentage of subjects who experienced the event. A subject reporting the same AE more than once will be counted only once when calculating (1) within a given system organ class and (2) within a given system organ class and preferred term combination. For such cases, the

maximum NCI-CTCAE toxicity grade and strongest causal relationship to study treatment for the event will be used in the incidence calculations. Treatment-emergent AEs will be tabulated to examine their frequency, severity, and relationship to study treatment. Additional summaries will be provided for SAEs and events resulting in the permanent discontinuation of treatment. All AEs will also be included in individual subject listings.

A listing of subjects who experience a DLT during the DLT assessment period of the dose- escalation portion will be generated along with the results associated with the PK/PDn parameters considered.

Laboratory parameters will be summarized using descriptive statistics and by postdose shifts relative to baseline. Vital sign results will also be summarized descriptively for each scheduled protocol time point. Changes will be calculated relative to the values collected at baseline, defined as the last assessment taken prior to the first dose of study drug on Day 1 of Cycle 1.

The analysis of the locally performed ECGs will involve descriptive statistics.

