2 STUDY OVERVIEW

2.1 Overall Study Design

This study is an open-label, Phase 1b/2, multicenter study in which subjects will receive oprozomib (OPZ) administered orally once daily in combination with dexamethasone (DEX) on 2 different treatment schedules. Subjects will receive OPZ on Days 1–5 of a 14-day cycle in combination with 20 mg DEX on Days 1, 2, 8, and 9; or OPZ on Days 1, 2, 8, and 9 of a 14-day cycle in combination with 20 mg dexamethasone on Days 1, 2, 8, and 9. Both the Phase 1b and Phase 2 portions of this trial will be open to subjects with relapsed and/or refractory multiple myeloma.

Treatment will be administered in 14-day cycles until disease progression, unacceptable toxicity, or study treatment discontinuation for any reason.

Disease response assessments will be performed every 4 weeks for the first year through Cycle 26 and then every 8 weeks thereafter according to the IMWG-URC. In addition, nCR and MR will be assessed per the modified EBMT criteria.

A minimum of 3 subjects will be entered within each dose cohort, to be expanded up to 6 subjects if DLTs are observed. Assessment of DLTs will occur during the first 14 days of treatment (or Cycle 1) or the first 14 days of treatment with the step-up dose to be

studies (Cycle 2). Any subject who develops a DLT after receiving at least 1 dose of OPZ will be considered evaluable. Any subject who does not develop a DLT, but has not received all planned doses of OPZ and DEX will be considered unevaluable for the dose escalation decision and will be replaced.

If none of the first 3 subjects in a cohort experiences a DLT in the first cycle, enrollment will commence at the next planned dose level. If 1 of 3 subjects enrolled in a cohort experiences a DLT during the first treatment cycle, the same cohort will be expanded up to 6 evaluable subjects. If 1 of 6 subjects experiences a DLT during the first treatment cycle, the next cohort will enroll at the next higher dose level. If 2 or more subjects in a cohort experience a DLT in the first treatment cycle, the MTD will have been exceeded, additional enrollment within the cohort will cease, and dose escalation will stop.

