Summaries that are displayed by system organ class and preferred terms will be ordered by descending order of incidence of system organ class and preferred term within each system organ class for the total group. Summaries of TEAEs, treatment-related AEs will also be provided by descending order of incidence of preferred terms in the total group.

All AEs, including TEAEs, will be included in listings by subject.

Listings of AEs determined to be DLTs during the first cycle of Phase 1, serious AEs, and AEs leading to discontinuation of study drug will be provided.

A summary of the number of deaths and the cause of death, classified by deaths within 30 days of last dose of study drug and deaths more than 30 days after the last dose, will be provided.

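### The SAP's only named DLT listing is limited to the first cycle, but for step-up cohorts the DLT window is Cycle 2

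*SAP*

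**What the plan says.** SAP 7.6.1 provides for "Listings of AEs determined to be DLTs during the first cycle of Phase 1", alongside listings of serious AEs and of AEs leading to discontinuation. No other DLT listing or table is named in the SAP.

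Protocol 10.3.3 describes the corresponding output differently: "A listing of subjects who experience a DLT during the DLT assessment period" of the dose-escalation portion.

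The protocol defines that period the same way in several places:

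- Section 6.3 counts events in the first 14 days "with treatment at the dose to be studied (i.e., Cycle 1 for continuous dosing or Cycle 2 for step-up dosing").
- The Phase 1b primary endpoint in 10.1 uses "14 days Cycle 1 for continuous dosing and Cycle 2 for step-up dosing".
- Section 3.1.2 says of the step-up cohorts: "The DLT period will begin in Cycle 2 (the first cycle of dosing at the step-up dose level").
- The footnotes to Tables 4 and 5 say: "Dose-limiting toxicity period will be 1 cycle (Cycle 1 for continuous dosing or Cycle 2 for step-up dosing").

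SAP 2.1 also recognises the later window. It assesses DLTs in Cycle 1 or in "the first 14 days of treatment with the step-up dose to be" studied, which it labels Cycle 2. Its 3+3 rules then use *first cycle* once and *first treatment cycle* three times, with no distinction by dosing type. SAP 3.1 gives the primary endpoint window as one 14-day cycle, without the Cycle 1/Cycle 2 qualifier in protocol 10.1.

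**The concern.** The SAP's wording for this listing conflicts with the protocol and with SAP 2.1. Step-up cohorts are within the SAP's scope: SAP 1 says it was prepared under Amendment 3, and protocol section 1 credits that amendment with introducing step-up dosing.

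If a programmer follows SAP 7.6.1 as written, the dedicated listing for a Phase 1b primary endpoint would show no DLTs in any step-up cohort, however many occurred. A reader of the abbreviated report could take the blank as evidence of tolerability at the step-up doses. The other AE listings are not specified to mark which events were DLTs, so they would not clearly correct that impression.

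**Working it through.** The plan states no figure for this point, so the check compares windows and then sizes the consequence.

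**1. Overlap of windows.** Inputs: 14-day cycles (protocol 3.1), the DLT windows in protocol 6.3, and the listing window in SAP 7.6.1 read literally as Cycle 1. With nominal cycles, Cycle 1 is days 1–14 and Cycle 2 is days 15–28.

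| Dosing | DLT window | Literal listing window | Window days covered |
|---|---|---|---|
| Continuous | days 1–14 | days 1–14 | 14 of 14 |
| Step-up | days 15–28 | days 1–14 | 0 of 14 |

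**2. Can any step-up DLT enter the listing?** There are two cases. An AE in the lead-in cycle falls inside the listing window, but protocol 6.3 does not count it as a DLT because the subject is not yet at the dose under study. An AE in Cycle 2 can be a DLT, but falls outside the listing window. Neither case yields an entry.

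**3. How many subjects are involved?** The firmest number is in protocol 3.1.2, for the 5/14 ER tablets: "The first cohort will enroll 6 subjects using step-up dosing". Tables 4 and 5 show further step-up cohorts, but the Table 4 footnote calls its scheme an example, so no larger count is used here.

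**4. Chance that the cohort of 6 has a DLT.** The documents give no DLT count for step-up cohorts, so a per-subject risk p has to be assumed. The range is 10% to 33%, the upper end being the protocol's MTD ceiling. All 6 subjects are assumed evaluable and independent. Expected subjects with a DLT = 6p; P(at least one) = 1 − (1 − p)^6.

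| Assumed p | 6p | 1 − (1 − p)^6 |
|---|---|---|
| 0.10 | 0.60 | 1 − 0.90^6 = 0.469 |
| 0.20 | 1.20 | 1 − 0.80^6 = 0.738 |
| 0.33 | 1.98 | 1 − 0.67^6 = 0.910 |

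On the literal reading these DLTs would all be left out, so the last column is also the chance that the listing misses at least one from this cohort.

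**5. With the protocol's window.** Using Cycle 1 for continuous and Cycle 2 for step-up dosing, coverage becomes 14 of 14 days for both.

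**The case against.** The strongest reply is that *first cycle* is shorthand for the first cycle at the dose under study. Protocol 3.1.2 describes Cycle 2 in just those terms for step-up cohorts. The four similar phrases in SAP 2.1 follow directly after a paragraph that states the Cycle 2 window, and read literally they would contradict it. The listing covers AEs already determined to be DLTs, a status the protocol definition sets. SAP 1 also promises to document departures from the protocol's analyses, and none is declared for DLTs. Taken together, this points to loose drafting, not a deliberate narrowing.

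That account of intent is fair, and no intended narrowing is alleged. It does not repair the text. SAP 7.6.1 ties the cycle to Phase 1, not to the step-up dose, and the SAP nowhere defines the shorthand. A programmer has to guess, and one of the two guesses empties the listing for step-up cohorts.

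The reply is also right that the consequence is limited. All AEs are listed by subject (SAP 7.6.1), eCRF and derived data are listed (SAP 7.1), and the Cohort Safety Review Committee decides escalation from the clinical data (protocol 6.2.1, SAP 8.2). No estimate, test or MTD rule depends on this listing. The probabilities above rest on assumed risks and apply only under the literal reading.

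**Conclusion.** The concern holds as a wording conflict with a possible reporting consequence, and it should be fixed. The textual mismatch is certain. The zero coverage of the step-up window follows from it only if the SAP is read literally, and the 47% to 91% figure further assumes a DLT risk of 10% to 33% in 6 evaluable subjects. What is at risk is the identification of step-up DLTs in the one output the SAP names for a Phase 1b primary endpoint. The events themselves would not be lost from the report. Whether the listing as produced omits anything cannot be told from the documents.

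**What to change.** - **SAP 7.6.1:** define the listing by the DLT assessment period, meaning Cycle 1 for continuous dosing and Cycle 2 for step-up dosing, as in protocol 10.3.3 and 6.3.
- **SAP 2.1:** bring the four first-cycle phrases in the 3+3 text into line with the window stated earlier in that section.
- **SAP 3.1:** add the Cycle 1/Cycle 2 qualifier from protocol 10.1 to the endpoint definition.
- **Existing output:** Amendment 4 says the analysis and abbreviated report are complete, so check the DLT listing already produced against this window. Issue a corrected listing only if step-up DLTs are missing.

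The cost is a line in SAP 7.6.1, matching words in SAP 2.1 and 3.1, and one check of an existing listing. No new data are needed and no estimate or test changes.

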7.6.2 Laboratory Data

All available laboratory results will be included in the subject data listings.

Selected laboratory test results will be assigned toxicity grades using CTCAE 4.03. A summary of post-baseline grade 3 or higher laboratory toxicities will be provided. The laboratory parameters of interest for these summaries are:

Hematology (all decrease)	Serum Chemistry (increase except where noted)	
Hemoglobin	ALT	Albumin
Platelets	AST	Uric Acid
WBC	Alkaline Phosphatase	Sodium (increase, decrease)
Neutrophils (absolute)	Total Bilirubin	Phosphorus (decrease)
Lymphocytes (absolute)	Creatinine	Potassium (increase, decrease)
	Calcium (increase, decrease)	Magnesium (increase, decrease)
	Glucose (increase, decrease)	

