4.1 INCLUSION CRITERIA

1. Diagnosis of multiple myeloma with measurable disease as indicated by 1 or more of the following:
 - a. Serum M-protein \geq 500 mg/dL
 - b. Urine M-protein \geq 200 mg/24 hour
 - c. Only for subjects without measurable serum and urine M-protein, serum free light chain: Involved free light chain (FLC) level \geq 10 mg/dL, provided serum FLC ratio is abnormal
2. Patients requiring therapy who have relapsed and/or are refractory to their last therapy and have been treated with at least 1, but not more than 5, lines of multiple myeloma

- therapy. Prior therapy must consist of at least 1 regimen that included lenalidomide and/or bortezomib. Patients should be considered to be appropriate candidates for a clinical study by their treating physicians. Relapsed patients must have previously achieved \geq MR on at least 1 line of therapy as assessed by the treating physician. Refractory patients are allowed, but it is not required that patients be refractory to their last therapy. Primary refractory patients are allowed in the Phase 1b portion of the study only.
3. Males and females \geq 18 years of age
 4. Eastern Cooperative Oncology Group Performance Status (ECOG PS) 0–2
 5. Adequate hepatic function, with bilirubin \leq 1.5 times the upper limit of normal (ULN) in the absence of Gilbert’s disease or hemolysis, aspartate aminotransferase (AST) \leq 3 times ULN, and alanine aminotransferase (ALT) \leq 3 times ULN
 6. Absolute neutrophil count (ANC) \geq 1000 cells/mcL, hemoglobin \geq 7.0 g/dL, and platelet count \geq 30,000 cells/mcL:
 - a. Patients must not have received platelet transfusions for at least 1 week prior to Screening.
 - b. Screening ANC must be independent of granulocyte colony-stimulating factor (G-CSF) and granulocyte-macrophage colony-stimulating factor (GM-CSF) support for at least 1 week and of pegylated G-CSF for \geq 2 weeks prior to first dose.
 - c. Patients may receive red blood cell (RBC) transfusions or receive supportive care with erythropoietin or darbepoetin in accordance with institutional guidelines.
 7. Calculated or measured creatinine clearance (CrCl) rate of \geq 30 mL/min calculated using the formula of Cockcroft and Gault $[(140 - \text{age}) \times \text{mass (kg)} / (72 \times \text{serum creatinine mg/dL})]$. Multiply result by 0.85 if female.
 8. Uric acid, if elevated, must be corrected to within laboratory normal range before dosing

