- Febrile neutropenia: Any single temperature $\geq 38.3^\circ\text{C}$ or a sustained temperature of $\geq 38.0^\circ\text{C}$ for over 1 hour with \geq Grade 3 neutropenia (ANC < 1000 cells/mcL)
- Grade 3/4 thrombocytopenia
 - Grade 3 thrombocytopenia of any duration with Grade 2 bleeding or requiring platelet transfusion
 - Grade 4 lasting ≥ 7 days

- Grade 4 lasting < 7 days with Grade 2 bleeding, or if platelet counts are lower than 10,000 cells/mcL, requiring a platelet transfusion

Note: The following will not be considered a DLT:

- Grade 4 anemia
- Grade 4 thrombocytopenia lasting < 7 days with platelet counts above 10,000 cells/mcL without clinically significant bleeding and with or without transfusion

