6.4.1.1 Dose Modification for Hematologic Toxicities

[Table 7](#) summarizes hematologic toxicities and oprozomib dosing actions that should occur in the event of toxicities.

Table 7: Guidelines for Dose Modification for Hematologic Toxicities

Toxicity	Oprozomib Dosing Action
ANC \geq 500 cells/mcL	Continue at full dose
ANC < 500 cells/mcL for less than 7 days	Hold dose. When ANC \geq 500 cells/mcL, resume at full dose.
ANC < 500 cells/mcL for 7 days or longer	Hold dose. When ANC > 500 cells/mcL, resume at 1 dose decrement.
Grade 3 febrile neutropenia	Hold dose. When ANC \geq 1000 cells/mcL and fever has resolved, resume at 1 dose decrement.
Platelet count < 50,000 cells/mcL and \geq 25,000 cells/mcL without evidence of bleeding	Continue at full dose
Platelet count < 50,000 cells/mcL and \geq 25,000 cells/mcL with evidence of bleeding	Hold dose. When platelet count returns to > 50,000 cells/mcL and bleeding stops, resume at 1 dose decrement.
Platelet count < 25,000 cells/mcL for < 7 days without evidence of bleeding	Hold dose. When platelet count \geq 25,000 cells/mcL, resume at full dose.
Platelet count < 25,000 cells/mcL for \geq 7 days with or without evidence of bleeding	Hold dose. When platelet count \geq 25,000 cells/mcL, resume at 1 dose decrement.

ANC = absolute neutrophil count.

Additional guidance regarding hematologic toxicities and dosing actions is as follows:

- Non-treatment-related events: If the toxicity resolves to \leq Grade 1 or baseline and the toxicity is not treatment related, oprozomib may be restarted at the same dose level.
- If required by continued or recurrent toxicity, a second or third dose reduction may be permitted down to a minimum dose of 150 mg after discussion with the **Sponsor** medical monitor. If the subject has not had 3 reductions but is at a dose level of 150 mg, an additional reduction may occur via reducing dose intensity (see [Section 6.4.1](#)). No more than 3 dose reductions will be permitted in an individual subject on study; if toxicity continues, the subject should be removed from the study.
- If the subject tolerates the reduced dose for 1 cycle, the subject's dose may be escalated to the dose prior to the dose reduction.
- If there is no resolution of toxicity after 2 weeks of withholding treatment (up to 3 weeks if an infection is being treated), the subject will be discontinued from the study.

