1 INTRODUCTION

This statistical analysis plan (SAP) was prepared for an abbreviated clinical study report (aCSR) in accordance with Protocol ONX-2012-001, dated 26 June 2014 (amendment 3), and describes the analyses of data collected within the scope of the study. Any changes that are made to the planned analyses after the SAP is finalized, along with an explanation as to when and why they occurred, will be noted in the abbreviated clinical study report produced for the study. Any changes made to the planned analyses that are in the protocol will be identified and documented in this document.

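### SAP 7.6.2 drops the protocol's shift-from-baseline laboratory summary without recording the change, so Grade 3 platelet counts already present at entry are mixed with new ones

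*SAP*

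**What the plan says.** Protocol 10.3.3 (Safety Analysis) sets the laboratory analysis: "Laboratory parameters will be summarized using descriptive statistics and by postdose shifts relative to baseline".

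SAP 7.6.2 (Laboratory Data) lists all results by subject and then grades a selection: "Selected laboratory test results will be assigned toxicity grades using CTCAE 4.03". Platelets and hemoglobin are among the parameters. The only summary is: "A summary of post-baseline grade 3 or higher laboratory toxicities will be provided". There is no shift table, no column for baseline grade, and no condition that the grade must have worsened. The descriptive statistics are gone as well.

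SAP Section 1 makes a commitment about such differences: "Any changes made to the planned analyses that are in the protocol will be identified and documented in this document". No change to the laboratory analysis is recorded anywhere in the SAP.

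Protocol 4.1, inclusion criterion 6, sets the entry floors: "hemoglobin \geq 7.0 g/dL, and platelet count \geq 30,000 cells/mcL". Table 7 in protocol 6.4.1.1 has a platelet band just above its lowest one: "Platelet count < 50,000 cells/mcL and \geq 25,000 cells/mcL".

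**The concern.** A table of post-baseline Grade 3 or higher values can be read as toxicity arising on study only if subjects start below Grade 3, or if baseline grade is shown beside the result. For platelets neither holds. The entry floor lies inside what the protocol treats as the Grade 3 range, and the summary that would have shown baseline is no longer planned.

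Safety and tolerability is a primary endpoint in both phases. SAP 7.1 presents results by schedule and dose group, and Phase 1b groups hold 3 to 6 subjects. In groups that small, one subject with a low count at entry visibly moves the percentage, and the summary table gives the reader no means of seeing why.

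**Working it through.** The plan states no figure on this point. Its one design calculation, for the response-rate test, does not bear on it. The check is a comparison of texts followed by a short illustration.

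**Step 1. Is the shift summary really absent?** Protocol 10.3.3 plans descriptive statistics and shifts from baseline. SAP 7.6.2 plans listings and a Grade 3 or higher table. SAP 5.3 defines baseline, but 7.6.2 uses it only to fix what counts as post-baseline. The SAP follows Amendment 3. The Amendment 4 change log (Appendix N) lists no change to protocol Section 10, so nothing suggests that the shift plan was added after the SAP was written.

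**Step 2. Does entry overlap Grade 3?** Table 7 carries no grade labels, so the mapping is inferred by comparing it with the DLT rules in protocol 6.3:

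| Protocol 6.3 (graded) | Table 7 (counts) |
|---|---|
| Grade 4 thrombocytopenia for 7 days or more | below 25,000 for 7 days or more |
| Grade 3 thrombocytopenia with Grade 2 bleeding | 25,000 to below 50,000 with bleeding |

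On that mapping Grade 3 is 25,000 to below 50,000. The entry floor is 30,000, so 30,000 to below 50,000 is both eligible and Grade 3, a window of 50,000 − 30,000 = 20,000 cells/mcL.

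Neutrophils behave differently. Protocol 6.3 defines "Grade 3 neutropenia (ANC < 1000 cells/mcL", and the entry floor for ANC is also 1000, so an eligible count is not Grade 3. The documents give no grade cutoffs for hemoglobin or lymphocytes, so no claim is made for them.

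**Step 3. Follow one subject.** Platelets are 40,000 at baseline and 40,000 at each later visit. The post-baseline grade is 3 and nothing in 7.6.2 excludes it, so the subject is counted. A shift table would place the same subject in the cell for Grade 3 at baseline and Grade 3 at worst, which shows no worsening.

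**Step 4. What is reached?**
- Grade 4 platelets (below 25,000): not affected. A baseline count that meets the 30,000 floor cannot be Grade 4, so any Grade 4 value is a worsening.
- DLT and MTD decisions: not affected. They follow protocol 6.2.2 and 6.3, where a Grade 3 platelet count is dose-limiting only with Grade 2 bleeding or a platelet transfusion.
- Adverse event tables: not affected. SAP 7.6.1 counts a pre-existing event only if it worsens.
- The Grade 3 or higher platelet row of the 7.6.2 table: affected.

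**Step 5. Size.** One unworsened entrant adds 1/6 = 16.7 percentage points in a cohort of 6, or 1/3 = 33.3 in a cohort of 3.

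For a larger group, let q be the share entering with Grade 3 platelets, w the share of those who worsen to Grade 4, and t the rate of new Grade 3 or higher counts among the rest. Assume that every baseline Grade 3 subject has at least one later value still at Grade 3 or higher.

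- Table as planned: q + (1 − q)t
- Worsened values only: qw + (1 − q)t
- Excess: q(1 − w)

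The documents give none of q, w or t. As an illustration only, take the 46 subjects (6 + 40) of a recommended-dose group:

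| q (assumed) | w (assumed) | Excess, points | Excess subjects of 46 |
|---|---|---|---|
| 0 | any | 0 | 0 |
| 5% | 0 to 30% | 5.0 to 3.5 | 2.3 to 1.6 |
| 10% | 0 to 30% | 10.0 to 7.0 | 4.6 to 3.2 |
| 20% | 0 to 30% | 20.0 to 14.0 | 9.2 to 6.4 |

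For example, with q = 10% and t = 20% the planned table shows 0.10 + 0.90 × 0.20 = 28%. The worsened-only rate is 0.90 × 0.20 = 18% if w = 0, and 0.10 × 0.20 + 0.18 = 20% if w = 20%.

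**The case against.** The strongest reply is that the table claims very little. It attributes nothing to treatment. Relatedness is handled in the adverse event tables, and protocol 9.1 keeps laboratory findings out of those unless they need corrective action or are judged clinically significant. All results are listed by subject, so in a cohort of 6 a reader can look up the baseline count. The SAP serves an abbreviated report, where some reduction is to be expected. The rule that unworsened values are counted is read from the absence of any exclusion, and the Grade 3 mapping is inferred from two parallel sets of rules.

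Much of this stands, and it limits what may be concluded. A reader might infer that the plan reports pre-existing cytopenia as drug toxicity; the table makes no causal statement, so the documents do not support that. A reader might connect the point to the Grade 4 thrombocytopenia DLTs described in protocol 1.4.3, but the entry floor keeps those outside its reach. It would also be too strong to say that the SAP contradicts itself because its adverse event rule requires worsening and its QTc summary (7.6.4) includes increase from baseline. These are different summaries under different rules.

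What the reply does not answer is the omission. Listings do not replace a summary that the protocol planned, and the SAP neither mentions the cut nor gives the abbreviated report as its reason.

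**Conclusion.** The point holds in a limited form. The protocol's shift-from-baseline laboratory summary is missing from SAP 7.6.2, and the departure is not recorded as SAP Section 1 requires. That part rests on the text alone and does not depend on how many subjects are affected.

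The consequence is that a subject who enters with platelets of 30,000 to below 50,000 and does not worsen is counted in the Grade 3 or higher platelet summary. This rests on two readings: that 25,000 to below 50,000 is Grade 3, inferred from Table 7 alongside the DLT rules, and that 7.6.2 applies no exclusion it does not state.

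The size is unknown, because the documents give no distribution of platelet counts at entry. It is zero if no such subject enrols and 17 percentage points per such subject in a cohort of 6. The figures for 46 subjects are illustrations on assumed inputs, and that group exists only if the sponsor opens Phase 2 for the schedule. This is a reporting defect worth correcting. It is no threat to the dose decisions.

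**What to change.** In SAP 7.6.2, restore a summary of shifts from baseline for the listed parameters. A table of baseline grade by worst post-baseline grade, in each direction listed, would show Grade 3 or higher values that worsened separately from those already present at baseline. Protocol 10.3.3 asks only for shifts relative to baseline and prescribes no layout, so this is one suitable form. With that table in place, the existing Grade 3 or higher summary can stay.

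Appendix N says that the primary analysis and the abbreviated report are complete. In that case, issue the shift table as a supplement and record the departure from protocol 10.3.3 with its reason.

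The cost is one standard table from data already collected and a short note of the change. No new visits or samples are needed.
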